#### 14.2 SUBJECT CONFIDENTIALITY

Subjects will be assigned a site/subject number to maintain subject confidentiality. Subject names may possibly be disclosed to AMO or regulatory agencies during inspection of medical records related to the study, but reasonable precautions will be taken to maintain confidentiality of personal information to the extent permitted by applicable laws and regulations.

#### 14.3 CASE REPORT FORM COMPLETION

This study will use an electronic data capture (EDC) system. The investigator is responsible for ensuring that data are properly recorded on each subject's case report forms and related documents. Prior to database lock, the investigator will verify completeness and accuracy of data submitted to AMO.

#### 14.4 STUDY SUMMARY

A final investigator's summary will be provided to AMO and the reviewing IRB within 3 months after termination or the completion of the study or the investigator's part of the investigation.

# 15. MONITORING

AMO will perform three types of monitoring to ensure compliance with regulations: data monitoring, administrative monitoring, and safety monitoring.

## 15.1 DATA MONITORING

In order to ensure a well-controlled clinical trial, AMO will follow specific data monitoring procedures. Following review of EDC data, requests for data clarification will be handled through the EDC data system. To minimize data omissions and inconsistencies on clinical reports and to ensure that data are accurately transcribed to computer data files, AMO will follow internal data processing procedures that include automated and manual

17NOV2015/ 3.0 PR/STAR-115-MIPS

quality control checks to identify any data discrepancies. Any such items will be resolved and documented as needed on the case report forms at the investigative site and in the data management system at AMO. Ongoing data review for clinical data monitoring will be conducted and will include evaluation of outliers for visual acuity and refractions as well as review of adverse event listings.

# **Prevention of Missing Data**

Methods used to safeguard against missing data that can have deleterious effects on the study integrity and reliability of its outcomes will include training study staff with centralized and on-site programs. In addition, subjects will be encouraged at the time of informed consent to avoid missing study visits, as missing data may affect the study reliability and diminish the scientific value of their contribution to the study.

#### 15.2 ADMINISTRATIVE MONITORING

Administrative monitoring procedures will ensure that study devices (e.g., key cards), subjects, and forms can be traced and will allow monitoring of the study site progress and compliance.

# **Device Accountability**

Use of the iDesign study device, the STAR-S4-IR laser and the STAR-S4-IR key cards used in this study will be tracked by the investigative site and AMO. Key card accountability will be maintained at the investigative on a site log to track disposition/return to AMO. During periodic investigative site monitoring visits AMO will review investigative site records and logs.

## Site Monitoring Plan

Prior to performing any study treatments, the requirements of the study and reporting mechanisms will be explained to each investigator either personally at the investigative site or at a formal study investigator meeting. When necessary, a pre-study site qualification visit may be performed to assess the adequacy of the site to perform the study for sites that have not previously worked with AMO or have undergone significant changes, or have not been visited in the past year. A study initiation visit will be conducted for all sites prior to or at the time of the first treatment.

Throughout the duration of the study, site visits to monitor compliance to this protocol will be made at each investigative site. During a routine site monitoring visit, AMO will review informed consent documents and subject eligibility, and the data on study case report forms will be verified against subject charts and other source documents to ensure complete and accurate reporting. The subject files will also be reviewed to assure that all adverse events and any issues encountered with AMO products have been reported in a timely fashion.

17NOV2015/ 3.0 PR/STAR-115-MIPS

AMO will also review source documents to verify that all required items have been documented in the subject medical charts. Refer to Section 14.1, Source Documents, for a list of items that are required for source documentation. In addition to subject files, study logs will be checked and conformance to lighting levels for visual acuity tests will be verified. Training on study-specific procedures may also be conducted during monitoring visits as necessary.

Upon study completion, a final close-out site visit to each site will be made to monitor the last of the subject data records and finalize any outstanding study issues.

A separate Study Monitoring Plan will be established prior to study start that will define the type and frequency of monitoring visits and frequency of record monitoring.

#### 15.3 SAFETY MONITORING

The medical monitor will review results throughout the clinical trial as necessary to ensure the continued safety of the device and to ensure that no subjects are exposed to unreasonable risk. The medical monitor will be available to answer questions from investigators. The medical monitor will review and assess any reports of serious and/or device-related adverse events as well as device deficiencies that could have led to a serious adverse event, and discuss these with the reporting investigator(s) as necessary. The medical monitor, as well as any other qualified personnel designated by AMO, shall also review any interim progress reports, as applicable.

## 16. PUBLICATIONS

Refer to the Cooperative Research and Development Agreement (CRADA) for information regarding AMO publication policies.

#### 17. RISK ANALYSIS

# POTENTIAL RISKS AND RISK MANAGEMENT

The safety and effectiveness of an iDesign System guided PRK treatment with the STAR Excimer Laser System, as well as long-term effects of PRK surgery in general, have not been fully determined. Unexpected complications or side effects may occur. As with any surgery or investigational procedure, all potential risks cannot be identified.

There may be complications and adverse events during or following the surgery which may be temporary or permanent. These may include pain, infection, foreign body sensation, dryness, fluctuation or decreased vision, change in visual quality, glare, halos, double vision, photophobia, transient light sensitivity syndrome, haze, corneal scarring and other medical findings, over- or under-correction, irregular astigmatism, corneal transplant, or blindness. Additional medications or surgeries may be required to treat these complications/adverse events.

17NOV2015/ 3.0 32 PR/STAR-115-MIPS

#### RISK MANAGEMENT

Subjects will be closely monitored thought the trial duration. The occurrence of adverse events and complaints will be assessed at each study visit and reported to AMO according to Section 11.0, Adverse Events and Product Complaints. Additionally, AMO will monitor incoming data following the procedures outlined in Section 15.0, Monitoring. The Medical Monitor will ensure subjects are not exposed to additional risks by monitoring serious adverse events, device-related adverse events, and device-deficiencies that could have led to serious adverse events (Section 15.3, Safety Monitoring).

## POTENTIAL BENEFITS

PRK treatment using the iDesign system in conjunction with the STAR S4 IR Excimer laser is expected to provide improved uncorrected distance visual acuity and accurate and stable refractive outcomes. Additionally, it is expected that the general clinical outcomes in this iDesign PRK study for the treatment of myopia with or without astigmatism will be similar to results obtained for the iDesign LASIK study for treatment of myopia with or without astigmatism, which has been submitted as a panel-track PMA supplement (P930016/S044).

# CONCLUSION

The hazards/risks associated with Advanced CustomVue Treatment using the iDesign Advanced WaveScan Studio System in conjunction with the STAR S4 IR Excimer laser are acceptable and expected to be similar to those of LASIK treatment using the iDesign System and STAR S4 IR Excimer laser. The potential clinical benefits of PRK treatment using the iDesign Advanced WaveScan Studio System in conjunction with the STAR S4 IR Excimer laser outweigh the residual risks when the device is used as intended.

#### 18. RECORDS RETENTION

All study-related correspondence, subject records, consent forms, Authorization for Use/Disclosure of Health Information Forms or similar medical treatment privacy law documentation, records of the distribution and use of all study products, and original case report forms should be maintained by the investigator.

The investigator must maintain and have access to the following essential documents until notified by the Sponsor. Note: This may be for a minimum of 15 years after completion of the study unless country-specific requirements are longer. AMO requires notification if the investigator wishes to relinquish ownership of the data so that mutually agreed-upon arrangements can be made for transfer of ownership to a suitably qualified, responsible person.

17NOV2015/ 3.0 PR/STAR-115-MIPS

- All case report forms
- All adverse event information (adverse event forms, follow-up letters, etc.)
- Investigational supply records/inventory
- IRB and regulatory approval documentation
- Study correspondence
- Study agreements
- Site visit documentation
- Protocol(s) and the reason for any deviations from the protocol
- Subject log(s)
- Clinical Investigator's Brochure
- Completed subject informed consent forms and medical privacy forms (e.g., Authorization for Use/Disclosure of Health information or equivalent documentation necessary to comply with applicable privacy laws pertaining to medical treatment in the governing countries)
- Subject medical chart/clinic notes

## 19. TERMINATION OF THE INVESTIGATION

The clinical investigation will be suspended in the event of high levels of complications and/or adverse events that are unexpected in nature and/or severity and evaluated as to causality relative to the study device. The clinical investigation may be suspended if the Medical Monitor or IRB, upon review and evaluation of the clinical data, finds unacceptable clinical performance or the level of single or total complications and/or adverse events unacceptable for continuation of the investigation.

If causality is shown not to be related to the study device, the study may be resumed in accordance with the IRB and regulations of the FDA. The study will be terminated if causality is shown to be related to the study device.

Additionally, the investigator, or AMO, may stop a subject's participation at any time. AMO may also stop the study at any time for reasons it determines appropriate. If refractive stability is established prior to the 12-month visit, the study may be terminated before all subjects reach the final 12 month visit. However, no suspension of the study would be made to disadvantage the study subjects. In the event of an early termination of the investigation, the sponsor will notify study sites, IRBs and appropriate regulatory bodies of the termination. Subjects will be followed as appropriate.

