## Safety

## 1. MAINTENANCE OF BSCVA-LINES LOST

- Success criteria: <5% of eyes with a loss of >2 lines of BSCVA from preoperative
- Success criteria: <1% of eyes with haze beyond 6 months with loss >2 lines of BSCVA

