#### PERIODIC POSTOPERATIVE EXAMINATION PROCEDURES

Periodic examinations will be conducted at 1, 3, 6, 9, and 12 months after treatment. In the event that extended follow-up is not needed, the follow-up period may be reduced.

Note: Subjects are not to wear contact lenses postoperatively until after completion of the study. Wearing contact lenses may potentially cause wavefront or topography changes that may influence the visual acuity results. During the study, if correction is required, spectacles should be prescribed.

The following data shall be assessed and recorded during the periodic examinations, although not all are required at all periodic visits (see also **Appendix A**). General descriptions and requirements of the various tests are provided in **Appendix C**. Non-directed responses to the open-ended question "Are you having any difficulties with your eyes or vision?", followed by all patient reported outcome questionnaires, followed by the iDesign measurement, are to be administered first before any other ocular examinations. All non-contact procedures (e.g. topography and keratometry) will be performed before contact assessments (e.g. IOP and pachymetry). If required, cycloplegic refraction/fundus exam will be the final procedures performed at the study visits.

- Ocular and systemic medical history and concomitant medications
- Non- directed ocular/visual symptoms (from non-directed responses obtained from the open-ended guestion "Are you having any difficulties with your eyes or vision?").
- Binocular Subjective Questionnaires: OSDI, PRVSQ for PRK/LASIK, NEI-RQL-42 and exploratory Satisfaction Questionnaire (Note: For reliability validation purposes the PRVSQ will be completed by the subject at the visit and also at home 7 days after the 3-month visit and mailed back to the site.)
- iDesign System Measurement (refraction, aberrometry, topography, keratometry, pupillometry)
- Keratometry (iDesign and auto/manual)
- Corneal Topography (Humphrey/Zeiss Atlas or Pentacam)
- UCVA photopic, monocular, distance (ETDRS)
- UCVA photopic, binocular, distance (ETDRS)
- Manifest Refraction (ETDRS)
- BSCVA photopic, monocular, distance (ETDRS)
  - At 3 months or later, if there is a loss of 2 or more lines of BSCVA (≥ 10 letters)
    compared to the preoperative visit, a rigid contact lens over refraction should be
    performed to determine if the BSCVA loss is due to irregular astigmatism. If a

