#### 20.2 PRIMARY STUDY ENDPOINTS

All primary effectiveness and safety endpoints will be evaluated at the stability timepoint.

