#### SERIOUS, DEVICE-RELATED ADVERSE EVENTS

The proportion of eyes with serious, device-related adverse events will be <1% cumulatively. The number and proportion of eyes with serious, device-related adverse events throughout the study will be summarized.

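### Follow-up may be shortened on confirmed refractive stability with no minimum observation for the primary haze criterion, which could then be met on few eyes examined beyond 6 months

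*Protocol*

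**What the plan says.** Two provisions allow shorter follow-up. Protocol Section 19 states: "If refractive stability is established prior to the 12-month visit, the study may be terminated before all subjects reach the final 12 month visit". It then adds "However, no suspension of the study would be made to disadvantage the study subjects" and "Subjects will be followed as appropriate". Protocol Section 10.6, under the periodic examinations, states: "In the event that extended follow-up is not needed, the follow-up period may be reduced". It does not define when extended follow-up is unneeded.

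Protocol Section 6.1 makes this a primary safety criterion: "<1% of eyes with haze beyond 6 months with loss >2 lines of BSCVA". Protocol 20.2 and SAP 5.2 repeat it. Protocol 20.2 also states: "All primary effectiveness and safety endpoints will be evaluated at the stability timepoint". SAP Section 5 says the same, and SAP Section 1 ties reporting and submission to the time of refractive stability.

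Under Protocol 6.3, stability may be shown on the 1-to-3-month interval. It must be confirmed at least 3 months later in a subgroup described only as statistically adequate. The interim looks (Protocol 20.5, SAP 8) are set at 90% of treated subjects reaching months 3, 6, 9 and 12, and cover the stability criteria only. The safety population is every treated eye (Protocol 20.1, SAP 2.1). Imputation and worst-case analyses are planned for the primary effectiveness endpoints only.

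**The concern.** The haze criterion concerns a harm that, by its own definition, can be recorded only after 6 months. The option to shorten follow-up depends on refraction, and the planned looks that would inform it contain no haze data. No section ties that option to having examined eyes after 6 months, and none says how eyes without such an examination enter the haze proportion. With all treated eyes as the safety population, unexamined eyes can enlarge the denominator without being able to contribute an event. A result below 1% would then say little about late haze.

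Choosing a later evaluation visit for haze would not cure this alone: if follow-up has ended, there are few or no examinations to evaluate.

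**Working it through.** **The plan's own figure.** 300 evaluable eyes with 10% attrition: 300 / 0.90 = 333.3, rounded up to 334. This reproduces Protocol 20.6. It secures 300 eyes at the stability point, not after 6 months. The documents give no sample size or power for the haze criterion.

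**Timeline** (Protocol Table 1 and 6.3)
- One month is 4 weeks, so 6 months is week 24.
- Earliest stability visit: month 3, weeks 10–14.
- Earliest confirmation: the 6-month visit, weeks 20–26. Only visits in weeks 25–26 fall beyond week 24.
- First visit wholly beyond 6 months: month 9, weeks 35–43. That is 35 − 26 = 9 to 43 − 20 = 23 weeks after the 6-month visit.

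**How many eyes would have a 9-month visit at termination?** Accrual time is not given, so I assume uniform accrual over A weeks. If the study stops when a fraction f of subjects has reached the 6-month visit, with nominal visits at weeks 24 and 36:

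share seen at month 9 = max(0, f − 12/A)

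| f | A = 26 weeks | A = 52 weeks |
|---|---|---|
| 90% (the planned look) | 0.90 − 0.462 = 44% | 0.90 − 0.231 = 67% |
| 50% | 0.50 − 0.462 = 4% | 0.50 − 0.231 = 27% |
| 25% | 0% | 0.25 − 0.231 = 2% |

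At f = 90% the share is zero only if A is below 12 / 0.9 = 13 weeks. Across the visit windows this limit runs from 9 / 0.9 = 10 to 23 / 0.9 = 26 weeks.

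**What full observation would give.** With 300 eyes, 2/300 = 0.67% passes and 3/300 = 1.0% fails.
- Independent eyes, true rate 2%: P(breach) = P(X ≥ 3), X ~ Bin(300, 0.02), = 0.940.
- Fully concordant fellow eyes (150 subjects): one affected subject is 2/300 and passes; two are 4/300 and fail. P(X ≥ 2), X ~ Bin(150, 0.02), = 0.804.
- No events, one-sided 95% upper bound 1 − 0.05^(1/n): 0.99% for n = 300 and 2.0% for n = 150.

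**What partial observation gives.** Suppose m eyes are examined after 6 months but the denominator stays at 300. A breach still needs 3 events, now from m eyes. With independent eyes and a true 2% rate, P(X ≥ 3), X ~ Bin(m, 0.02):

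| m | P(breach) | Upper bound if 0 of m |
|---|---|---|
| 300 | 94% | 0.99% |
| 150 | 58% | 2.0% |
| 75 | 19% | 3.9% |
| 30 | 2% | 9.5% |
| 0 | 0 | none |

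If the denominator were all 334 treated eyes, 3/334 = 0.90% would pass, so a breach would need 4 events and each breach probability with eyes observed would be lower.

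**The case against.** The strongest reply is that the plan has more protection than the termination sentence suggests.

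- **Stability must be confirmed.** A reader might infer that the study can stop as soon as refraction is stable. It cannot by this route: confirmation comes at least 3 months later, and the rate-of-change and confidence-interval criteria must also hold. If stability falls at month 6, confirmation comes at about month 9, when the confirming eyes already have an examination beyond 6 months. The problem is therefore concentrated in the month-3 branch.
- **There is some protective wording.** A reader might infer that no safety condition exists at all. Section 19 does say that suspension would not disadvantage subjects and that they would be followed. This names no visit, duration or number of eyes, so it does not secure the haze data, but it is not nothing.
- **Some eyes would probably be seen.** A reader might infer that no eye would be observed beyond 6 months. That requires fast accrual or a small confirming subgroup. At the planned 90% look, about 44% or 67% of eyes would have a 9-month visit with 26 or 52 weeks of uniform accrual. Stopping on a small subgroup also sits poorly with the 90% looks, although those looks are optional.
- **Month-12 data are not simply lost.** Protocol 10.8 asks for a final visit with the 12-month procedures when a subject leaves early, Appendix A has an early-termination column, and a fundus examination is scheduled at month 6. Such a final visit may itself fall at or before 6 months.
- **Serious events.** "The proportion of eyes with serious, device-related adverse events will be <1% cumulatively" refers to events during the study, so a shorter study does not contradict that criterion.
- **Disclosure.** SAP 3.1 will report available eyes by visit, so a careful reader could see the shortfall. It would not change the stated pass or fail.

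No section states that unobserved haze will be recorded as absent. What stands is that no section prevents it, and none secures observation beyond 6 months.

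**Conclusion.** The concern holds in this form: early termination or reduced follow-up on confirmed stability, possible from about the 6-month visit if stability falls at month 3, carries no minimum follow-up for a primary safety criterion that exists only beyond 6 months. The criterion could be met on few informative eyes.

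The size cannot be fixed from the documents. Full observation would detect a true 2% rate with probability of about 80% to 94%, depending on fellow-eye concordance. With early termination and an unrestricted denominator, that protection falls with the number of eyes examined, and disappears if there are none. These figures assume 300 eyes as the full set; the partial-observation figures also assume independent eyes, and the accrual figures assume uniform accrual and nominal visit weeks.

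There is also a direct conflict. If the stability point is month 3, a criterion about haze beyond 6 months cannot be evaluated at that point, whether or not follow-up is later cut.

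**What to change.** Reconcile Protocol Sections 10.6 and 19, and the stability-time-point rule in Protocol 20 and 20.2 and SAP 5, with the haze criterion in Protocol 6.1 and 20.2 and SAP 5.2, so that the option to shorten follow-up cannot remove the observation the criterion needs. How that is achieved is for the sponsor and its clinical advisers.

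In Protocol 20.2 and SAP 5.2:
1. Evaluate the haze criterion on examinations after 6 months, as an explicit exception to evaluation at the stability time point. Without this exception, item 2 would leave an empty denominator when stability falls at month 3.
2. Use eyes examined after 6 months as the denominator.
3. Report that number and an exact confidence interval with the proportion.
4. State that the criterion is not evaluable, rather than met, if no eye was examined in that window. This also covers the sponsor's general right in Section 19 to stop the study for other reasons.

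The cost is wording in both documents. The haze denominator may be smaller than the safety population and the stated result less favourable, and reconciling the passages may limit the sponsor's freedom to end follow-up early.

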# 20. STATISTICAL METHODS

This section highlights the analyses for the primary and secondary study endpoints as well as the key safety endpoints. All endpoints will be evaluated at the refractive stability time point. Visual acuities will be converted to logMAR.

17NOV2015/ 3.0 34 PR/STAR-115-MIPS

